### **13.0 Risks to Subjects**

This is considered a minimal risk study. Minimal risk means the probability and magnitude of harm or discomfort anticipated in the research are not greater in and of themselves other than those ordinarily encountered in daily life or during performance of routine physical or psychological examinations or tests. The LTW screening tool is the same tool that is used in clinical practice, the only difference is in its delivery. The potential risks in this study include those related to: a) confidentiality; b) frustration; and c) emotional distress.

- a) Confidentiality:** Participants will be made aware of limits to confidentiality at the beginning of screening and when reviewing study procedures/during informed consent which include report of suicidal or homicidal intent or report of abuse or neglect. If the participant reports substance use during pregnancy or suicidal or homicidal intent or abuse/neglect, [name] will take appropriate action by completing a psychiatric assessment and facilitating appropriate treatment. Additional appropriate actions as outlined by the MUSC IRB, NIH, and the State of South Carolina, may also include contacting the department of social services, authorities and/or pursuing involuntary commitment at a mental health or substance use disorder treatment facility. If participants present no imminent danger but also need more extensive treatment of mental health or substance use concerns, appropriate care will be facilitated.
- b) Frustration:** Participants may become frustrated while completing study assessments. Participants will be informed that they may refuse to answer any question(s) that they do not wish to answer and that they may discontinue study participation at any time.
- c) Emotional Distress:** Participants will be asked questions that may be sensitive in nature. Participants may find the questions distressing or find the questions make them feel uncomfortable. Participants will be informed that they may refuse to answer any question(s) that they do not wish to answer and that they may discontinue study participation at any time.

Since patients will all currently be receiving prenatal care or will be currently postpartum, there are no additional risks associated with participation in this study.

### ***Adequacy of Protection Against Risks***

#### **Recruitment and Informed Consent**

Study participants will be recruited from local MUSC clinics. Pregnant and postpartum patients identified via the EMR through a recruitment report (research data request) will be sent a message inviting them to participate in a research study. Interested patients will complete determination of eligibility via MUSC's REDCap system, a secure, HIPAA-compliant data management system. All participants will review consent documents and will provide informed consent consistent with procedures outlined above. Participants will be given the opportunity to ask questions about their participation throughout the course of the study. A copy of the informed consent will be kept centrally at our study office within locked filing cabinets, and a copy will be given to each study participant as well. Participants will be given a study phone number and e-mail address to contact for questions.

#### **Protections Against Loss of Confidentiality**

All screening information will be kept in a password protected REDCap database. Only key study personnel will have access to the database. If an individual is not eligible to participate based on her answers to the eligibility survey, her screener will not include her name or contact information. Only people who meet eligibility criteria based on the answers to the eligibility survey will be asked if they would like to be contacted about participation in the study and for their name and contact information. Eligible participants' full name, telephone number and

e-mail address will be recorded in the study enrollment log located on a secure MUSC drive or in MUSC Box. The REDCap database and the study enrollment log are the only places where participants' names and subject identification numbers appear together. Eligible participants will be assigned a subject number, will complete informed consent, will be randomized, will complete baseline assessments, and subsequently will receive their randomized intervention.

Upon completing eligibility screening, if study eligible, individuals will be provided with an overview of the study, asked to review study procedures via a consent form, and asked to provide signed consent. Participants will be informed of limitations of confidentiality (i.e., abuse or neglect, intention to harm self or someone else) both verbally and/or in writing during the informed consent process. The consent form will include the participant's name, but not his/her subject number. Consent forms will be provided in English.

Regarding questionnaire data, data will be obtained for research purposes only. All data will be collected, stored, and managed via REDCap, which is a secure, web-based application designed exclusively to support data capture for research studies. REDCap provides secure, web-based flexible applications, including real time validation rules with automated data type and range checks at the time of entry. The underlying database is hosted in a secure data center at MUSC, a secure environment for data systems and servers on campus, and includes redundancy, failover capability, backups and extensive security checks. The system has several layers of protection including user/group account management, "Data Access Groups" which allow data to be entered by multiple groups in one database with segmented user rights for entered data, audit trails for all changes, queries and reports, and Secure Sockets Layer (SSL) encryption. Name and relevant contact information will be obtained to provide compensation and every effort will be made to maintain subject confidentiality, in accordance with HIPAA. All data will be identified only by code numbers (participant IDs). Participant IDs will be linked to participants' names in a password-protected file that is accessible only to the PI and trained research staff. Voice sample data gathered through SurveyLex for specific aim 1 participants only, will be stored on HIPAA compliant Microsoft Azure servers managed by NeuroLex. MUSC has a BAA in place with Neurolex. MUSC currently pays NeuroLex \$100/month for access to their software. MUSC may collect 5000 surveys per month. The data will consist of data tables containing the coded participant ID, date of the recording, voice features, and separates raw voice recording files. Data tables of voice features extracted from the recordings will have only the subject's coded participant ID, and no other identifying information. Access to the SurveyLex account will be limited to research study staff. Staff at NeuroLex will not access this data.

Voice features collected through SurveyLex will be downloaded and stored on an MUSC Box account, accessible only to study staff.

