\*\*Only participants in specific aim 2 complete the GAD-7, CSSRS and TLFB

\*\*\*Only participants assigned to LTW will complete the usability scale

+ As of the approval of amendment 10 newly enrolled participants will not complete CSSRS and TLFB. Participants consented prior to the approval of amendment 10 will complete CSSRS and TLFB at baseline.

Specific aim 3: We will gather healthcare utilization data on our study participants who have Medicaid insurance. The MUSC study team will extract the maternal Medicaid IDs from our study participants with Medicaid insurance from the EHR. We will share a list of these maternal Medicaid IDs with Medicaid, and they will return data related to maternal and newborn diagnosis codes, health care utilization and costs for these participants i.e., prenatal care visits, postpartum care visits, hospitalizations and ED visits during pregnancy and the postpartum year. The MUSC study team will send the maternal Medicaid ID's of study participants to Medicaid in a password protected spreadsheet. Medicaid will send the MUSC study team a password protected spreadsheet of data. The spreadsheet of data Medicaid will send back to MUSC will be coded since

it will contain the Medicaid ID's of participants.

The Medicaid ID is the only link to subjects in the study. The document linking Medicaid ID's and our study participants will be stored on a University secure network drive or in MUSC BOX. The linking document will be stored separately from the study data and only trained study personnel will have access to the linking document.

Study data will be stored on a University secure network drive or in MUSC BOX. The spreadsheet of data that Medicaid will send the MUSC study team will be password protected. Only trained study personnel will have access to the password protected data spreadsheet.

The MUSC study team will have access to the Medicaid ID's as well as Medicaid.

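### Reported substance use during pregnancy triggers action under section 13.0, but is not among the limits of confidentiality the protocol says women are told

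*Protocol*

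**What the plan says.** Two places in the Protocol describe what women are told about the limits of confidentiality.

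- **Section 13.0 Risks to Subjects, item a) Confidentiality.** "Participants will be made aware of limits to confidentiality at the beginning of screening" and again during consent. The limits are those "which include report of suicidal or homicidal intent or report of abuse or neglect".
- **Protections Against Loss of Confidentiality**, later in section 13.0. "Participants will be informed of limitations of confidentiality (i.e., abuse or neglect, intention to harm self or someone else". The disclosure is made verbally and/or in writing as part of informed consent, in which eligible women are "asked to review study procedures via a consent form, and asked to provide signed consent".

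Item a) then sets out what the study does with certain reports. The triggering clause is "If the participant reports substance use during pregnancy or suicidal or homicidal intent or abuse/neglect". The first response is a psychiatric assessment and help in obtaining treatment. Further steps, governed by rules from outside the protocol, come next: the text says that these "may also include contacting the department of social services, authorities and/or pursuing involuntary commitment", the last of them at a mental health or substance use disorder facility. Item a) ends by saying that where there is no imminent danger but more extensive care is needed, including for substance use, that care will be arranged.

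**The concern.** A woman deciding whether to answer a question about drug or alcohol use needs to know who may learn of the answer and what may follow. Items b) and c) of section 13.0 let her refuse any question, but that protection is weaker if she does not know what an answer can set in motion.

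The subject is central to this trial. The SBIRT screen asks about alcohol, cigarettes and other drugs, with the same tools in both arms (section 3.0). The NIDA Modified Assist is a baseline assessment (section 10.0). Recruitment uses diagnosis codes partly so that enough women with substance use disorders are approached (section 8.0). Such disclosures are therefore expected. If the consent form and the statement at the start of screening follow the protocol's wording, women would be asked about substance use without being told of a trigger on which the protocol itself acts.

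**Working it through.** No arithmetic applies to the main point, and the plan gives no figure to reproduce. The check is a comparison of text.

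**Step 1. Match each trigger to the disclosed limits.**

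| Trigger for action, 13.0 a) | Named in the limits in 13.0 a)? | Named in the limits under Protections Against Loss of Confidentiality? |
|---|---|---|
| Substance use during pregnancy | No | No |
| Suicidal or homicidal intent | Yes | Yes, as intent to harm self or another |
| Abuse or neglect | Yes | Yes |

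Two of the three triggers appear in both descriptions. The remaining one, substance use during pregnancy, appears in neither.

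**Step 2. Look for the limit elsewhere.** Section 9.0 Consent Process says that consent will stress the policy on privacy and confidentiality, but lists no limits, so it does not fill the gap.

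**Step 3. Read the actions against the triggers.** Item a) describes three levels of response.

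1. Assessment and facilitated treatment, for every trigger.
2. Possible further actions: social services, authorities, involuntary commitment. These are stated once for the whole group and are tied to outside rules ("Additional appropriate actions as outlined by the MUSC IRB, NIH, and the State of South Carolina") that are not reproduced in the documents.
3. Facilitated care where there is no imminent danger.

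The third level partly answers what happens to a woman who reports use and is in no danger. It does not make imminent danger a condition for contacting social services or the authorities, so it does not settle whether the second level can follow from substance use alone.

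**Step 4. Confirm that the question is still asked.** The footnotes to the section 10.0 assessment table say that, from amendment 10, new participants no longer complete the CSSRS and TLFB. The SBIRT screen and the NIDA Modified Assist remain, so substance use is still asked about.

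**Step 5. Bound the number of women.** Section 6.0 gives 100 + 350 = 450 to be randomised, which is the ceiling. Section 5.0 admits postpartum as well as pregnant women. The documents give neither the split nor the proportion expected to report use during pregnancy, so no estimate below that ceiling is offered.

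**The case against.** The strongest reply is that the two lists do different jobs. One gives limits of confidentiality; the other gives reports that prompt clinical action. Assessment and facilitated treatment do not in themselves breach confidentiality. That is correct, and it means the passages do not contradict each other. A reader might infer that the protocol is internally inconsistent, but the documents do not support so strong a reading. The list in 13.0 a) is introduced as an open one. The *i.e.* in the later passage cannot safely be read as closing its list either, because the protocol uses the term loosely elsewhere. In section 10.0 the Medicaid data are described as "i.e., prenatal care visits, postpartum care visits, hospitalizations and ED visits during pregnancy and the postpartum year", which leaves out the newborn care visits listed in section 4.0.

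Second, what women are actually told is set by the consent form and the start-of-screening statement. Neither was available, and either may already name substance use. This stands in full. A reader might infer that women are not warned; the documents do not show that.

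Third, the state, NIH and IRB rules that the protocol invokes are not in the documents. External action on substance use might arise only through the abuse-or-neglect limit, which is already disclosed. A reader might infer that reported use must be passed to the authorities, or equally that it never is. Neither can be established here. Listing substance use separately from abuse or neglect does not decide the matter.

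Fourth, the protocol is not silent on consequences. It names the further actions directly after the trigger list, and one of them refers to a substance use disorder facility. What is missing is only the link between each action and each trigger.

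After these concessions, one narrow point remains: the protocol's own account of what women are told omits a trigger on which it says the study will act.

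**Conclusion.** The point holds as a gap in participant-protection wording. Reported substance use during pregnancy is a stated trigger, further actions that could include outside agencies are named for the triggers as a group, and neither description of the disclosed limits mentions it. From the protocol alone, one cannot tell which of those further actions can follow from substance use alone.

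Its size is modest. Up to 450 women are to be asked, and the number affected is unknown. It rests on the protocol text as it stands and on the assumption that the participant-facing statements follow that text. If the consent form and the screening statement already name the limit, only the protocol needs to be brought into line.

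A reader might go further and infer under-reporting of substance use, or bias between the arms. The documents give no basis for that, and no effect on outcome data is claimed. This is a cheap improvement, not a defect that threatens the trial.

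**What to change.** Choose according to what the sponsor intends.

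- **If further action can follow from substance use during pregnancy:** add it, with the further actions that may follow, to the disclosed limits in section 13.0 a) and under Protections Against Loss of Confidentiality. Check that the consent form and the start-of-screening statement say the same in both arms.
- **If nothing beyond assessment and facilitated treatment is intended for substance use alone:** reword the further-actions sentence in 13.0 a) so that it applies only to the other triggers. The disclosed limits then need no addition.

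Either route is a minor amendment with IRB review. Under the first, stating the limit up front may slightly lower disclosure or enrolment.

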#### **14.0 Potential Benefits to Subjects or Others**

There is no direct benefit for subjects from participating in the study.

#### **15.0 Sharing of Results with Subjects**

Study enrollment and study outcomes will not be shared with medical staff, including the participant's physician.

Statistical Analysis Plan

Sample Size and Power Analysis

Using a chi-square testing framework and a significance level of 0.05 and assuming two-sided hypothesis testing, both primary and secondary outcomes included a large enough sample size to detect differences between groups. Our a priori group sample sizes (usual care: n=191; LTWP: n=224) provided 80% power to detect between-group absolute differences in proportions ranging from 6% to 12% in the primary study outcomes (for example, screened: 65.2% [usual care] versus 77.7% [LTWP]; screened positive: 21.7% versus 34.2%, respectively; referred: 12.5% versus 23.1%, respectively; and attended treatment: 2.1% versus 8.3%, respectively). Our group sample sizes among participants completing a screen (usual care: n=63; LTWP: n=221) provided 80% power to detect between-group absolute differences in proportions ranging from 11% to 18% in the secondary study outcomes (for example, screened positive: 17.5% [usual care] versus 35.4% [LTWP]; referred: 3.2% versus 15.3%, respectively; and attended treatment: 1.6% versus 12.3%, respectively). The usual care rates used in these calculations were based on data published from earlier work on the LTWP program.

Data Analysis

We will assess the adequacy of randomization by comparing LTWP versus usual care (UC) on demographic, obstetric, and psychiatric baseline characteristics, using t-tests or Wilcoxon rank sum tests for continuous variables and chi-square tests or Fisher's exact tests for categorical variables, respectively. Descriptive statistics will be calculated for each screening method (LTWP versus usual care), including counts and percentages for participants who were screened, screened positive, referred to treatment, and attended treatment. Unadjusted differences in outcomes between people assigned to LTWP versus UC will be calculated using chi-square tests because all study outcomes are dichotomous. Relative risk (RR) ratios will be estimated and reported along with their 95% confidence intervals. All hypothesis tests will be two-sided with a type 1 error set at 0.05, and all analyses will be performed using SAS statistical software, version 9.4 (Cary, NC).

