**Specific Aim 2:**

**Primary Outcome:**

Attendance to Treatment: treatment attendance (defined as attending at least 1 or more visits with a mental health and/or substance use disorder (SUD) treatment provider during pregnancy and the postpartum year)

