## **6.0 Number of Subjects**

A total of 450 participants will be randomized in Specific Aim 1 (n=100) and Specific Aim 2 (n=350). To randomize 450 participants we will need to approach about 1,500 participants in order to get to 450 total participants.

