## **10.0 Study Design / Methods**

Specific aim 1: A two arm pilot RCT (N=100) with 2:1 allocation will examine feasibility and preliminary efficacy of LTW, compared to TAU. Specific aim 2: A RCT (N=350) with 2:1 allocation will examine effectiveness of LTW, compared to TAU. As of the approval of amendment #12 the allocation will switch to 1(LTW):2(TAU) for specific aim 2. Recruitment will primarily occur proactively and remotely via the EHR. We will conduct a weekly EHR search via a recruitment report for all new pregnant and postpartum patients in the past week. The report will include mrn, age, race, ethnicity, date of prenatal care visit, date of postpartum visit, delivery date, ob/gyn provider name, MyChart account (Yes/No), cell phone number, email address and current ICD-9 or 10 diagnoses. Any patients who have not opted out of being contacted for research will be contacted and invited to participate. The study team will not cold-contact any patients who have chosen to opt-out of receiving contact about research or who have met the maximum number of contact attempts at the time of recruitment. If the potential participant has not opted out of being contacted, or the potential participant's provider has agreed to have the study team contact their patient, a phone call will be made or message will be sent via text, email or MyChart message to the potential participant inviting them to take part in the study. This invitation will include clear opt out procedures should the patient not wish to be contacted in the future for the purpose of this study. If interested, participants will complete a screening online via REDCap to determine study eligibility (see above for inclusion criteria). After completing preliminary determination of eligibility, if eligible and interested in participating in the study, participants will be scheduled for a time to complete informed consent (see 9.0 Consent Process).

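### The SAP's 80% power reproduces, but it rests on 415 women whom the protocol does not plan and on two usual-care input sets that cannot describe one population

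*SAP*

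**What the plan says.** The SAP's power section uses a two-sided chi-square test at 0.05. For the primary outcomes it says "Our a priori group sample sizes (usual care: n=191; LTWP: n=224) provided 80% power to detect between-group absolute differences". Its example rates include "screened: 65.2% [usual care] versus 77.7% [LTWP]; screened positive: 21.7% versus 34.2%, respectively", then 12.5% against 23.1% referred and 2.1% against 8.3% attended.

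For the secondary outcomes it says "Our group sample sizes among participants completing a screen (usual care: n=63; LTWP: n=221) provided 80% power", with "screened positive: 17.5% [usual care] versus 35.4% [LTWP]; referred: 3.2% versus 15.3%, respectively", and 1.6% against 12.3% attended. One sentence gives the source for both sets: "The usual care rates used in these calculations were based on data published from earlier work on the LTWP program".

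Protocol Section 6.0 says "A total of 450 participants will be randomized in Specific Aim 1 (n=100) and Specific Aim 2 (n=350". Section 10.0 starts both aims at 2:1 and adds "As of the approval of amendment #12 the allocation will switch to 1(LTW):2(TAU) for specific aim 2". Section 4.0 makes the Aim 2 primary outcome "treatment attendance (defined as attending at least 1 or more visits with a mental health and/or substance use disorder (SUD) treatment provider"; visits count from pregnancy to the end of the first year after delivery.

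**The concern.** The SAP concludes from these figures that the sample was large enough for primary and secondary outcomes alike. Two features make that hard to rely on.

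- **Size.** The group sizes are presented as fixed in advance, yet their sum is neither the Aim 2 size nor the total. No exclusion or dropout allowance connects them. Power for attendance, the Aim 2 primary outcome, is not stated at the 350 women planned for that aim.
- **Inputs.** Only a screened woman can screen positive. In one population, the positive rate among women screened therefore cannot be lower than the rate among all randomised. The SAP's usual-care figures have it lower.

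At stake is whether the stated 80% applies to the trial that the protocol describes.

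**Working it through.** **Method.** p1, n1 are usual care and p2, n2 are LTWP:

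- power = Φ[(|p2 − p1| − 1.96·s0)/s1]
- s0 = √[p̄(1 − p̄)(1/n1 + 1/n2)], with p̄ = (n1·p1 + n2·p2)/(n1 + n2)
- s1 = √[p1(1 − p1)/n1 + p2(1 − p2)/n2]

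**1. Reproduce the SAP.** Attendance at 191/224: s0 = 0.02235, s1 = 0.02115, so (0.062 − 1.96 × 0.02235)/0.02115 = 0.860 and power is 80.5%.

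| Set | Screened | Positive | Referred | Attended |
|---|---|---|---|---|
| Primary, 191/224 | 80.6% | 80.8% | 80.3% | 80.5% |
| Completers, 63/221 | – | 80.2% | 80.4% | 80.4% |

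**2. Place 415 against the protocol.** 191 + 224 = 415, which is 65 above 350 and 35 below 450. The ratio 224/191 = 1.17 is neither 2:1 nor 1:2. Pooling both aims could produce it. For example, 100 Aim 1 women and 157 Aim 2 women at 2:1, then 158 at 1:2, give 66.7 + 104.7 + 52.7 = 224 LTWP women of 415. Neither document says that this was done.

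**3. Power at the planned sizes, with the SAP's primary differences.** I assume that the initial 2:1 favours LTW, as the later switch implies. Let m of Aim 2's 350 women be randomised at 2:1 and the rest at 1:2, so LTW = 2m/3 + (350 − m)/3. For 450, add Aim 1 (66.7 LTW, 33.3 usual care). The documents do not give m, so the range covers m = 0 to 350.

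| N | Screened | Positive | Referred | Attended |
|---|---|---|---|---|
| 350 | 67.5-73.8% | 68.1-74.3% | 66.7-74.0% | 64.4-75.4% |
| 450 | 80.0-83.8% | 79.1-84.3% | 78.1-83.9% | 77.0-84.7% |

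Exact enumeration for attendance runs higher: 66.9-80.5% at N = 350, against 83.4% at 191/224.

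**4. Compare the two usual-care sets.**

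- Screened: 0.652 × 191 = 124.5 women, against 63 completers (63/191 = 33.0%).
- Positive: 0.217 × 191 = 41.4 women among all randomised, against 0.175 × 63 = 11.0 among completers.
- Rates among women screened, implied by the primary set: 0.217/0.652 = 33.3% positive, 0.125/0.652 = 19.2% referred, 0.021/0.652 = 3.2% attended. The completer set has 17.5%, 3.2% and 1.6%.
- The primary set follows the in-person rates in Protocol Section 2.0: 65.2% × 33.33% = 21.7%; × 57.63% = 12.5%; × 16.04% = 2.0% (SAP: 2.1%). The completer set does not.

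**5. Completer power with the primary-implied usual-care rates,** at the SAP's completer differences (17.9, 12.1 and 10.7 points). This assumes that unscreened women are neither referred nor attend.

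| Usual care / LTWP completers | Positive | Referred | Attended |
|---|---|---|---|
| 63 / 221 (SAP counts) | 72% | 46% | 71% |
| 125 / 221 | 90% | 69% | 93% |
| 125 / 174 (77.7% of 224) | 87% | 66% | 90% |

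**The case against.** Four points on the other side carry weight.

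- **63 may be a realised count.** The SAP's power section is in the past tense. If 63 was observed, its gap from 65.2% of 191 is a departure from a planning rate and not a contradiction. That stands, but then 63 and 221 are not planning inputs and should not be presented beside sizes set in advance.
- **The source sentence names no single publication.** Two earlier cohorts could both satisfy it. A reader might infer that the attribution is false for one set, or, since 17.5%, 3.2% and 1.6% equal 11/63, 2/63 and 1/63, that trial results were fed into the power calculation. The documents prove neither.
- **Holding 63 fixed mixes the two sets.** A reader might take 72/46/71% to mean that completer power fails on all three outcomes once the primary usual-care rates are used. It does not. Those rates come with about 125 usual-care completers, and two of the three outcomes then exceed 80%.
- **Attendance in Aim 2 does not require screening.** Section 4.0 sets no such condition, so unscreened women may count. At 63/221, attendance regains 80% if about 48% of usual-care attendances came from unscreened women. Referral would need about 83%.

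It is also fair to say that 415 exceeds 350, so the calculation cannot be for Aim 2 alone as planned, and that pooling is the more natural reading. The SAP still has to say so. The gap between 221/224 and 77.7% in the LTWP arm is not pressed, because the LTWP rates look like solved detectable values and not assumptions.

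**Conclusion.** The point holds as a mismatch of inputs, not an arithmetic error.

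- **Set covered.** By the method that reproduces the SAP, 80% is too high for Aim 2 alone (64-75%; attendance at most 75.4%) and about right for all 450 (77-85%). Exact enumeration for attendance at 350 just reaches 80.5% at the most favourable mix, so too high for Aim 2 is a general statement and not an absolute one.
- **Completers.** The two usual-care sets cannot describe one population. The positive rates show this without further assumption. Of the three completer outcomes, only referral is below 80% in every combination tried (46-69%), and that assumes unscreened women are not referred.

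A reader might infer that the trial is underpowered. The documents do not support that: the pooled total keeps roughly the stated power, and no test or endpoint is affected. The correction is worth making because the adequacy claim cannot at present be tied to a planned set of women.

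**What to change.** Change the SAP wording only:

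1. Name the randomised set covered, either Aim 2 alone or Aims 1 and 2 pooled, and reconcile 415 with 350 and 450, including any exclusions and the allocation mix.
2. Restate power for that set, and give power for attendance in Aim 2 at 350.
3. Say whether 63, 221 and the completer usual-care rates were planned or observed, and where each comes from.
4. Delete the completer power sentence, or recompute it from one coherent set of usual-care rates and completer counts, stating whether unscreened women can count as referred or attended.

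No patients are added. The cost is that some stated power figures may fall: the primary outcomes if the set is Aim 2 alone, and at least the completer referral outcome if the primary usual-care rates are used and unscreened women do not count as referred.
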